9.3. Variables

The key vaccine exposure, baseline, and safety outcome variables are listed in Table 1. Detailed definitions are provided in [Section 9.3.1](#).

Table 1. Key vaccine exposure, baseline, and safety outcome variables to be collected in this study

Variable	Role	Data Source(s) ^a
Date of index date dose COVID-19 vaccination	Exposure	Participant and/or their designee
Location where index date dose COVID-19 vaccine was administered	Exposure	Participant and/or their designee
Vaccine lot number (index date dose)	Exposure	Participant and/or their designee
Anatomical site where index date dose COVID-19 vaccine was administered	Exposure	Participant and/or their designee
Date of all subsequent dose(s) COVID-19 vaccination(s)	Exposure	Participant and/or their designee
Location where all subsequent COVID-19 vaccine dose(s) was/were administered	Exposure	Participant and/or their designee
Vaccine lot number (all subsequent doses)	Exposure	Participant and/or their designee

090177e1991e3913Approved\Approved On: 18-Jan-2022 22:29 (GMT)

Table 1. Key vaccine exposure, baseline, and safety outcome variables to be collected in this study

Variable	Role	Data Source(s)^a
Anatomical site where all subsequent COVID-19 vaccine(s) was/were administered	Exposure	Participant and/or their designee
Demographics	Baseline characteristics	Participant and/or their designee
Medical History	Baseline characteristics	Participant and/or their designee
Employment characteristics	Baseline characteristics	Participant
Concomitant medications and other vaccines	Baseline characteristics	Participant and/or their designee
Participant reported safety event of interest (described in Section 9.3.1)	Outcome	Participant and/or their designee
Validated safety event of interest	Outcome	Health care provider (HCP) questionnaire or medical record review
Participant reported hospitalization (date and length of admission)	Outcome	Participant and/or their designee
Validated hospitalization (date and length of admission)	Outcome	Health care provider questionnaire or medical record review
Participant's designee reported death (date)	Outcome	Participant's designee
Validated death (date)	Outcome	Health care provider questionnaire or medical record review
Pregnancy status and last menstrual period (LMP) (if applicable)	Baseline characteristics	Participant, their designee, or medical record review

090177e1991e3913\Approved\Approved On: 18-Jan-2022 22:29 (GMT)

Table 1. Key vaccine exposure, baseline, and safety outcome variables to be collected in this study

Variable	Role	Data Source(s) ^a
Pregnancy outcomes (if applicable)	Outcome (live birth, preterm birth or still birth) ^b	Participant, their designee, or medical record review

- a. Designee may include HCP or study staff administering the vaccine.
 b. Pregnancy outcomes will be collected during study follow-up period.

9.3.1. Safety Outcome Definitions

Data on medically attended safety events of interest will be collected from the time of participants' enrolment into the study until death, withdrawal of consent, loss to follow-up or end of study period, whichever occurs first.

Medically attended safety events of interest in this study are listed in Table 2. These events are based on the AESI lists developed by ACCESS and SPEAC/Brighton Collaboration, which consists of events previously identified with immunization in general (e.g. anaphylaxis, GBS), with vaccine platforms relevant to COVID-19 vaccine development, or with theoretical concerns based on immunopathogenesis or viral replication during wild type disease (4, 5).

Participant reported medically attended safety events of interest will be followed up with the treating HCPs or through medical record documentation if needed to validate or establish the diagnosis associated with the event and validate the occurrence of a safety event of interest, or other clinically significant event. Additional safety events may be added as endpoints based on emerging findings from clinical studies, spontaneous reports, literature or updates in guidance.

Table 2. Medically attended safety events of interest^a

Body System	Safety Event
Neurologic	Generalized convulsion/ seizure
	Guillain-Barré Syndrome (GBS)
	Aseptic meningitis
	Encephalitis / Encephalomyelitis
	Other acute demyelinating diseases
	Transverse myelitis
	Multiple sclerosis
	Optic neuritis

090177e1991e3913\Approved\Approved On: 18-Jan-2022 22:29 (GMT)

Table 2. Medically attended safety events of interest^a

Body System	Safety Event
	Bell's palsy
	Acute disseminated encephalomyelitis
Immunologic	Anaphylaxis
	Vasculitides*
	Arthritis and arthralgia
	Multisystem inflammatory syndrome in adults (MIS-A)
	Kawasaki disease
	Fibromyalgia
	Autoimmune thyroiditis
COVID-19	Severe COVID-19 disease * **
	Acute respiratory distress syndrome
	Microangiopathy*
	Heart failure and cardiogenic shock*
	Stress cardiomyopathy*
	Coronary artery disease*
	Arrhythmia*
	Deep vein thrombosis
	Pulmonary embolus
	Cerebrovascular stroke
	Limb ischemia*
	Hemorrhagic disease*
	Acute kidney injury*
	Acute liver injury
	Chilblain-like lesions
	Single organ cutaneous vasculitis*
	Erythema multiforme*
	Anosmia, Ageusia
	Acute pancreatitis

090177e1991e3913\Approved\Approved On: 18-Jan-2022 22:29 (GMT)

Table 2. Medically attended safety events of interest^a

Body System	Safety Event
	Rhabdomyolysis
	Subacute thyroiditis
Cardiac	Myocarditis
	Pericarditis
	Acute myocardial infarction
	Microangiopathy
	Heart failure
	Stress cardiomyopathy
	Coronary artery disease arrhythmia
Hematologic	Thrombocytopenia
	Disseminated intravascular coagulation
	Coagulation disorder (includes thrombotic disorders, bleeding disorders)
Other	Death
	Narcolepsy and cataplexy
	Non-anaphylactic allergic reactions
	Reactogenicity 
 • Injection site reaction (redness, warmth, pain, itch, hematoma, swelling, induration) • Fever/feverishness • Shivering/chills • Headache • Vomiting and Diarrhoea • Myalgia/muscle pain • Arthralgia/joint pain • Malaise • Fatigue

a. The medically attended safety events of interest in this study are based on the adverse events of special interest (AESI) defined by ACCESS as well as the Coalition for Epidemic Preparedness (CEPI)-funded Safety Platform for Emergency vACCines (SPEAC) working with the Brighton Collaboration. Additional medically attended safety events of interest may be identified as information emerges about events potentially related to vaccines. Details on risk windows for events will be detailed in the SAP.

Table 2. Medically attended safety events of interest^a

Body System	Safety Event
-------------	--------------

* Hospitalized manifestations only.

** All hospitalized COVID-19 disease will be assessed for vaccine-associated enhanced disease.

9.4. Data sources

Scheduled assessments for the study are presented in the Data Collection Schedule provided in [Table 3](#) below. Participant informed consent must be obtained before any data are collected.

Baseline data will be collected via an electronic Case Report Form (eCRF). At baseline, data listed in [Section 9.4.1](#) will be collected directly from the persons receiving the vaccine and/or their designee; this may include HCP or study staff administering the vaccine. Data describing vaccine administration on that date will also be collected.

For follow-up data, standard questionnaires will be completed by participants or their designees online or via the mobile app. The data listed in [Section 9.4.2](#) will be collected. Telephone interviews will use a standard script for interviews. Both data collection methods will include information that reported medically attended safety events of interest and laboratory confirmed COVID-19 infections may trigger additional follow-up to obtain further information.

Participant reported medically attended safety events of interest will be reviewed and additional safety data will be collected from HCPs if needed to validate or establish the diagnosis associated with the event and validate the occurrence of the reported safety event or other clinically significant events. A standard questionnaire will be used for this follow-up.

Participants will be asked to report any subsequent COVID-19 vaccine received during the follow-up period. The data to be collected is listed in [Section 9.4.3](#).

If the participant fails to submit follow-up data / is non-responsive to follow-up reminders or telephone calls, follow-up with a secondary contact will be conducted (as per [Section 9.2.3](#)) in order to determine whether non-response is due to a safety event of interest.

Table 3. Data Collection Schedule.

	Baseline	Each subsequent vaccine dose	Follow-up at weeks 1, 2, 4, 6, 8 and 12 following each Pfizer-BioNTech COVID-19 mRNA vaccine dose	Quarterly follow-up until 24 months following index date, or end of study, whichever occurs first
Informed consent	X			
Demographics	X			
Medical history	X	X		
Concomitant medication and other vaccines	X	X		
Pfizer-BioNTech COVID-19 mRNA vaccine information	X	X		
Pregnancy status (if applicable)	X	X	X	X
Occurrence of medically attended safety events of interest			X	X
Pregnancy outcomes (if applicable)			X	X
Contact information and preferred follow-up method	X	X	X	X
Reason for discontinuation from study (if applicable)			X	X

9.4.1. Baseline Assessment (vaccine dose received at index date)

The following data will be collected at baseline for all enrolled participants (further details in [Annex 3](#)):

1. Informed consent.
2. Unique identifier.
3. Demographics (age, gender, ethnicity, occupation).

4. Medical history, if available, including:
 - Allergies to medication,
 - Pre-existing co-morbidities, including (but not limited to) chronic obstructive pulmonary disease (COPD), diabetes, chronic neurological disease, cardiovascular disorders, autoimmune or inflammatory disorders,
 - Indicators of frailty³,
 - Whether the participant is immunocompromised for any reason,
 - Presence of potential active viral disease within previous 3 days (fever, symptoms of cold, flu, or other inflammatory/infectious process),
 - Information of any prior laboratory confirmed diagnosis of COVID-19,
 - COVID-19 vaccination history prior to index date dose, including date(s) of previous immunization(s), dose(s), and manufacturer,
 - Pregnancy status (female participants of childbearing potential only).
5. Any concomitant medication taken within the 7 days prior to vaccination, if available, including prescription and non-prescription medication (e.g. herbal or homeopathic medication) as well as medication with long half-life or long-term effect (e.g. immunoglobulins, blood transfusions, immunosuppressants), and any other vaccines received.
6. Vaccination information (of index date Pfizer-BioNTech COVID-19 mRNA vaccine dose), including date of immunization, dose, lot number, anatomical site of injection.
7. Contact information (which may include telephone number and/or email address) for:
 - The participant,
 - A secondary contact for the participant [for follow-up purposes only],
 - Primary care physician [for follow-up purposes only].
8. Preferred participant follow-up method – telephone interview or web/app-based questionnaire.

³ Indicators of frailty will be collected via two means: (1) directly from participants, during completion of the baseline questionnaire, and (2) from the treating health care provider during follow-up of safety events of interest reported by the participant. To collect indicators of frailty directly from participants, the PRISMA 7 questionnaire will be used for participants aged 65 years and over, and all participants will be asked a question on Self-Reported Health. See [Annex 3](#) for further questionnaire details.

9.4.2. Weekly, monthly, and long-term follow-up, through 24 months following the index date vaccine dose

The following data will be collected directly from participants at pre-specified follow-up points outlined in the data collection schedule (further details in [Annex 3](#)):

1. Pregnancy status (female participants of childbearing potential only), and pregnancy outcomes (as applicable).
2. Details of medically attended safety events of interest, including laboratory confirmed diagnosis of COVID-19, since the last follow-up.
3. Any changes in contact information.
4. Changes in preferred follow-up method – telephone interview or web/app-based questionnaire.
5. Discontinuation data will be collected for all enrolled participants at the time of discontinuation:
 - Date of discontinuation.
 - Number of vaccine doses received at the time of discontinuation.
 - Reason for discontinuation.

Data on reactogenicity will be collected only during week 1 following each Pfizer-BioNTech vaccine dose.

9.4.3. Each subsequent COVID-19 vaccine dose during the follow-up period

Participants will be asked to report any subsequent COVID-19 dose received during the follow-up period (further details in [Annex 3](#)).

The following information will be collected at all subsequent COVID-19 vaccine doses (irrespective of whether the vaccine received was the Pfizer-BioNTech COVID-19 mRNA vaccine or another COVID-19 vaccine):

1. Vaccine manufacturer.
2. Date of immunization.
3. Pregnancy status (female participants of childbearing potential only).
4. Any changes in contact information.
5. Changes in preferred follow-up method – telephone interview or web/app-based questionnaire.

If the vaccine received was the Pfizer-BioNTech COVID-19 mRNA vaccine, the following information will also be collected:

6. Additional vaccination information, including dose, lot number, anatomical site of injection.
7. Changes in prior submitted medical history, including any other vaccines received, and concomitant medication use within the 7 days prior to vaccination, if available.

9.5. Study size

The primary objective of this study is to quantify the incidence of medically attended safety events of interest by estimating their incidence rates per 10,000 person-years, calculated as the number of participants experiencing the event after receiving a dose of the Pfizer-BioNTech COVID-19 mRNA vaccine during the person-time at risk (numerator) divided by the total person-time at risk (denominator).

The target for enrolment will be approximately 13,334 participants (vaccine recipients). Table 4 provides illustrative examples of expected margin of error ([width of confidence interval/2]) for different incidence rates per 10,000 person-years. The margin of error was calculated for a range of attrition rates (25%, 40%, and 55%) for illustrative purposes.

Table 4. Margin Of Error Scenarios For Targeted Sample Size And Different Incidence Rates Over A 24-Month Follow-Up Period

Target n	Attrition rate assumption	Expected n who complete 24 months follow-up	Incidence rate (per 10,000 person-years)	95% Confidence intervals (exact) according to different incidence scenarios	Margin of error
13,334	25%	10,000	1	[0, 3]	1.5
			5	[3, 9]	3.0
			10	[6, 15]	4.5
			50	[41, 60]	9.5
			250	[230, 271]	20.5
			500	[472, 530]	29.0
			2500	[2436, 2565]	64.5
			5000	[4910, 5092]	91.0
	40%	8,000	1	[0, 4]	2.0
			5	[2, 10]	4.0

Table 4. Margin Of Error Scenarios For Targeted Sample Size And Different Incidence Rates Over A 24-Month Follow-Up Period

Target n	Attrition rate assumption	Expected n who complete 24 months follow-up	Incidence rate (per 10,000 person-years)	95% Confidence intervals (exact) according to different incidence scenarios	Margin of error
			10	[5, 17]	6.0
			50	[39, 64]	12.5
			250	[223, 279]	28.0
			500	[462, 540]	39.0
			2500	[2414, 2588]	87.0
			5000	[4878, 5124]	123.0
	55%	6,000	1	[0, 6]	3.0
			5	[1, 12]	5.5
			10	[5, 20]	7.5
			50	[37, 68]	15.5
			250	[218, 286]	34.0
			500	[454, 549]	47.5
			2500	[2396, 2607]	105.5
			5000	[4853, 5151]	149.0

The 95% confidence intervals are derived using the (exact) Clopper and Pearson method.

Calculations were done in R Version 4.0.2.

Further analyses described in [Section 9.7](#) for secondary endpoints will be exploratory in nature and will not involve formal hypothesis testing. The statistical analysis plan (SAP) will expand the statistical methods mentioned in [Section 9.7](#) of this protocol.

090177e1991e3913\Approved\Approved On: 18-Jan-2022 22:29 (GMT)

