9.2. Setting

This primary data collection study will aim for up to 10,000 vaccine recipients with 2 years of follow-up data. In order to reach this estimated sample size of vaccine recipients with complete data, 13,334 participants will be targeted for enrolment, assuming a 25% dropout rate over the 2-year follow-up period. The study will be conducted in Germany, Italy and Spain in a total of approximately 20 centers. Other countries may be included in addition to, or as a replacement, for one or more of these countries, as required to fulfill study objectives.

It is anticipated that participants will be enrolled from settings based upon the regional availability and distribution of vaccine according to national or regional COVID-19 preparedness plans and may include physician offices, hospitals, pharmacies, and/or vaccination centers. Site selection criteria will include the projected availability of eligible participants in the enrolment period and the availability of physician (and other site staff) time to complete brief baseline case report forms (CRFs) where required. Selection criteria and basic site information (e.g. site size, site type) will be collected via a site qualification survey.

Limited inclusion/exclusion criteria will be applied in this study, to ensure comprehensive capture of individuals receiving the Pfizer-BioNTech COVID-19 mRNA vaccine in real-world settings.

Participants will be considered enrolled if they meet the inclusion/exclusion criteria below, have provided informed consent (as required per local regulations), and have reported the date of Pfizer-BioNTech COVID-19 mRNA vaccination at baseline.

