9.7. Data analysis

The study population of Pfizer-BioNTech COVID-19 mRNA vaccine recipients will be described in terms of demographic characteristics (age, gender, ethnicity, occupation) and medical history characteristics outlined in [Section 9.4.1](#). Vaccination characteristics, including number of doses received and interval between doses, will also be described.

The incidence rates of medically attended safety events of interest and corresponding 95% Poisson exact confidence intervals (95% CI) will be estimated in the primary safety dataset of participants who enroll within 2 days of vaccination. Rates will also be estimated for the overall study population and within subcohorts of interest such as pregnant vaccine recipients, immunocompromised participants, and within age-categories.

A final analysis will also be conducted for the following subcohorts of interest, given the potential for mixed exposure:

1. **Pfizer-BioNTech vaccine only**: all participants who only receive Pfizer-BioNTech COVID-19 mRNA vaccine(s), and no other COVID-19 vaccine(s), prior to index date and during their follow-up period.
2. **Heterologous vaccination**:
 - a) **Pfizer-BioNTech booster(s) only**: all participants who received only Pfizer-BioNTech COVID-19 mRNA vaccine dose(s) as booster dose(s) during the study period, but where the primary vaccine course (prior to index date) was non-Pfizer-BioNTech.
 - b) **Heterologous primary course**: all participants who received Pfizer-BioNTech COVID-19 mRNA vaccine as a first dose at index date, and then received a non-Pfizer-BioNTech second dose during their follow-up period. No booster doses were received.
 - c) **Other combination heterologous vaccine course/booster**: all participants with a heterologous primary course and/or heterologous booster dose(s), who do not fit the criteria for inclusion in subcohorts 2(a)-(b) above.

It is anticipated that rates will be reported for the following intervals, overall and for each of the subcohorts of interest:

- Follow-up at weeks 1, 2, 4, 6 and 8 following a Pfizer-BioNTech COVID-19 mRNA vaccine dose,
- Quarterly follow-up following a Pfizer-BioNTech COVID-19 mRNA vaccine dose (until 24 months following index date vaccine dose, or end of study, whichever occurs first).

[figure not shown]

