
Primary study objective:
 
Estimate the real-world incidence of medically attended safety events of interest and other clinically significant events among individuals vaccinated with the Pfizer-BioNTech COVID-19 mRNA vaccine after approval in the EU.
	
Medically attended safety events of interest, and other clinically significant events
	
Incidence rates per 10,000 person-years and corresponding 95% Poisson exact CI. Incidence rates precision estimates as provided in Section 9.5.

Secondary objective:
 
Evaluate whether the vaccine recipients experience increased risk of medically attended safety events of interest post-vaccination, via comparison with expected background rates and, as feasible, by self-controlled risk interval (SCRI) analysis.
	
Medically attended safety events of interest
	
OE analysis: Safety event of interest (observed) incidence rates in cohort of study participants compared to background (expected) incidence rates, obtained from the EMA-funded COVID-19 vaccine monitoring ACCESS program or, if unavailable, from historical or concurrent rates reported in the literature.
 
SCRI analysis: Incidence rate ratio (IRR) of medically attended safety events of interest occurring in the risk interval versus the control period, estimated by conditional Poisson regression models. Sensitivity analysis for SCRI: considering different lengths of the risk and control intervals.

090177e1991e3913\Approved\Approved On: 18-Jan-2022 22:29 (GMT)

Table 5. Planned analysis by study objective

Objective	Outcome of interest	Planned analysis

Secondary objective:
 
Estimate the incidence rates of medically attended safety events of interest among sub-cohorts of interest such as pregnant vaccine recipients, immunocompromised participants, and stratified by age.
	
Medically attended safety events of interest
	
Incidence rates per 10,000 person-years and corresponding exact Poisson 95%CI*:
 
 • Among sub-cohort of pregnant vaccine recipients, • Among sub-cohort of immunocompromised participants, • Stratified by age: 18-29; 30-39; 40-49; 50-59; 60-69; 70-79; 80 and above.

European Union (EU); 95% Poisson exact confidence intervals (95% CI); self-controlled risk interval (SCRI); incidence rate ratio (IRR).

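### The 40% and 55% attrition blocks of Table 4 rest on fewer person-years than their own completers would supply, and the footnote names the wrong interval method

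*Protocol*

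**What the plan says.** Section 9.2 of the protocol fixes the base case: "13,334 participants will be targeted for enrolment, assuming a 25% dropout rate over the 2-year follow-up period". Section 9.5 then presents Table 4, titled "Margin Of Error Scenarios For Targeted Sample Size And Different Incidence Rates Over A 24-Month Follow-Up Period", and explains: "The margin of error was calculated for a range of attrition rates (25%, 40%, and 55%) for illustrative purposes". The table has one target n, 13,334, for all three blocks. Its expected completers are 10,000 (25% attrition), 8,000 (40%) and 6,000 (55%). The margin of error is defined as half the width of the confidence interval. The footnote states: "The 95% confidence intervals are derived using the (exact) Clopper and Pearson method".

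Section 9.7 and Table 5 plan Poisson exact intervals for the incidence rates. For the primary objective, Table 5 refers back to the study-size section: "Incidence rates precision estimates as provided in Section 9.5".

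**The concern.** If the same 13,334 people are enrolled in each scenario, moving from 25% to 40% or 55% attrition should widen the intervals only moderately, because people who drop out still contribute person-time before they leave. The printed widening is much larger. At a rate of 5,000 the margin goes from 91.0 to 123.0 and then 149.0.

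The study has no power calculation, so Table 4 is the only quantitative support for its size. Two of the three scenarios would give a wrong picture of how much precision poor retention costs. The footnote would also send anyone checking the table to a binomial method that does not return its figures and is not the planned analysis.

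**Working it through.** **Inputs.** From Section 9.5: 13,334 enrolled; attrition of 25%, 40% and 55%; 24 months of follow-up (2 person-years, PY, per completer); the printed limits. The completer counts check: 13,334 × 0.75, 0.60 and 0.45 give 10,000, 8,000 and 6,000 after rounding. The protocol does not state the person-time credited to a drop-out. One year each (half the period) is inferred below.

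**Formula.** Events x = rate × PY / 10,000, rounded to an integer. Exact Poisson limits per 10,000 PY are ½χ²(0.025; 2x)/PY × 10,000 and ½χ²(0.975; 2x+2)/PY × 10,000.

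**Step 1: reproduce the 25% block.** PY = 10,000 × 2 + 3,334 × 1 = 23,334. At a rate of 5,000, x = 11,667 and the limits are [4910, 5092], margin 91.0, as printed. All 16 limits in the block match.

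**Step 2: same rule for the other blocks.**
- 40%: 8,000 × 2 + 5,334 × 1 = 21,334 PY. Only 1 or 2 of 16 printed limits match, depending on how events are rounded.
- 55%: 6,000 × 2 + 7,334 × 1 = 19,334 PY. Only 1 of 16 matches.

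**Step 3: find the PY that the printed limits imply.** A search over PY matches all 16 limits only within 12,708–12,802 (40%) and 8,700–8,719 (55%). Completers alone would give 8,000 × 2 = 16,000 and 6,000 × 2 = 12,000. The printed blocks therefore rest on less person-time than their own completers supply, whatever is assumed about drop-outs.

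**Step 4: likely mechanism.** Entering the completers as enrolled and applying attrition again gives:
- 40%: 4,800 × 2 + 3,200 × 1 = 12,800 PY (16 of 16 match).
- 55%: 2,700 × 2 + 3,300 × 1 = 8,700 PY (16 of 16 match).

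**Step 5: size of the error.** Margins from rounded limits, with attrition applied once to 13,334 and half-period credit:

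| Rate per 10,000 PY | 40% printed | 40% recomputed | 55% printed | 55% recomputed |
|---|---|---|---|---|
| 50 | 12.5 | 10.0 | 15.5 | 10.0 |
| 250 | 28.0 | 21.5 | 34.0 | 22.5 |
| 500 | 39.0 | 30.0 | 47.5 | 32.0 |
| 2,500 | 87.0 | 67.0 | 105.5 | 71.0 |
| 5,000 | 123.0 | 95.0 | 149.0 | 100.0 |

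At high rates the ratios are √(21,334/12,800) = 1.29 and √(19,334/8,700) = 1.49. For rates up to 50, against unrounded recomputed margins, the excess ranges over about 20–34% (40% block) and 51–66% (55% block), because event counts are small integers. With no credit for drop-outs, the margins at 5,000 would be 110.0 and 127.0: 123.0/110.0 = 1.12 and 149.0/127.0 = 1.17.

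**Step 6: interval method.** Clopper-Pearson on 23,334 at a rate of 5,000 gives [4936, 5064], not the printed [4910, 5092]. On the same denominators as above it matches at most 11, 9 and 9 of 16 limits in the three blocks. Exact Poisson matches 16 in each.

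**The case against.** **The affected blocks do not set the study size.** The 25% block does, and it is right. The other two are described as illustrative, and no target or decision rule uses them. The error also runs in the safe direction: true precision is better than printed. All of this stands. A reader might infer that the study-size justification fails or that the study is too small; the documents do not support that.

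**Double attrition is not the only explanation.** The amendments section describes the Table 4 update in terms of population size and recruitment as well as retention. If 8,000 and 6,000 were meant as numbers enrolled, the printed margins are right and the labels are wrong. That reading remains open, although 13,334 × 0.60 and × 0.45 giving exactly the printed completer counts speaks against it. On either reading, labels and figures disagree.

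**The recomputed margins rest on an unstated assumption.** Half-period credit is inferred from the 25% block. This affects the 29% and 49%, but not the contradiction in Step 3 or the footnote error.

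**The primary analysis set.** A reader might also fault Table 4 for using all enrolled, since rates "will be estimated in the primary safety dataset of participants who enroll within 2 days of vaccination". That is not an error in the table: its title refers to the targeted sample size, Section 9.7 also estimates rates in the overall study population, and the protocol gives no figure for the share enrolling within 2 days.

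**Conclusion.** The point holds, limited to two defects in Table 4.

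First, the 40% and 55% blocks contradict their own labels on any assumption about drop-outs. If 13,334 enrolled is what was meant, the printed margins are too wide by about 29% and 49% at high rates under half-period credit, and by about 12% and 17% if drop-outs are given no credit. Attrition applied twice is the likely cause, not a proven one.

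Second, the footnote misnames the method. The printed limits are Poisson exact and agree with Section 9.7 and Table 5, so the planned analysis is not in question.

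The consequence is modest. The loss of precision from poor retention is exaggerated, while the base case and the enrolment target stand.

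**What to change.** - Recompute the 40% and 55% blocks from 13,334 enrolled (21,334 and 19,334 PY under half-period credit). If lower recruitment was meant, relabel them instead as 8,000 and 6,000 enrolled with 4,800 and 2,700 completers, and keep the printed limits.
- Add a person-years column and state the person-time assumed for a drop-out.
- Change the footnote to Poisson exact.

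The cost is a re-run or relabelling of two blocks and one footnote, with no change to enrolment, conduct or analysis. Rows for participants enrolled within 2 days would be a useful option, with the assumed share stated, but are not needed to correct the error.
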